APPENDIX B. SCHEDULE OF ASSESSMENTS: OBSERVATION PERIOD AND SAFETY FOLLOW-UP

Visit (weeks)	Observation Period							Safety Follow-up ^a
	Week 1		Week 3	Week 6	Week 12	Week 18	Week 24/ EOT	
Visit (days)	Day 1 ^b	Day 7	Day 21	Day 42	Day 84	Day 126	Day 168	Day 196
Visit to investigational site	X	X	X	X	X	X	X	X
Weight/BMI							X	X
Vital signs ^c		X	X	X	X	X	X	X
ECG (12-lead) in triplicate ^d					X		X	X
Physical examination ^e							X	X
Urine pregnancy test (females of child-bearing potential only) ^f		X			X		X	
Blood for hematology and chemistry		X	X	X	X	X	X	X
Urinalysis							X	
Erythropoietin							X	
RBC deformability, dense cells (if feasible)					X		X	
Hemoximetry (P50 and P20) ^g		X	X		X		X	
Study drug administration ^{h,i}	→							
Blood for PK assessment ^j		X	X		X		X	
CGI-C and PGI-C					X		X	
Concomitant medications		X	X	X	X	X	X	X
Adverse events		X	X	X	X	X	X	X

BMI = body mass index; CGI-C, Clinical Global Impression of Change; ECG, electrocardiogram; EOS, End of Study; EOT, End of Treatment; P20, partial pressure at which hemoglobin is 20% saturated with oxygen; P50, partial pressure at which hemoglobin is 50% saturated with oxygen; PGI-C, Patient Global Impression of Change; PK, pharmacokinetic; RBC, red blood cell.

Note: For procedures scheduled to be performed at the same timepoint, the order of assessments is as follows: vital signs, PK sample collection, blood draw for PD/safety laboratory assessments, ECGs. If times are delayed due to technical difficulties, this will be noted but not considered a protocol violation. RBC deformability and dense cells will be tested if feasible by the local or collaborating lab at the time of collection.

^a Safety Follow-up visit will take place 28 days post final dose.

^b Day 1 of the observation period is the same as the last day of the dose escalation period. If the participant begins the observation period after a dose reduction, a Day 1 clinical visit is needed, which would collect the same assessments as the Day 21 visit in the Dose Escalation Period (Appendix A).

^c Vital signs (heart rate and blood pressure) will be obtained in the morning prior to dosing and other planned assessments.

^d Single safety ECG at Week 12, Week 24/ET, and Week 196 (EOS).

^e Physical examinations may be abbreviated. Abbreviated physical examination should include at a minimum: Examination of skin, cardiovascular and respiratory systems, abdominal examination, and symptom-directed examination.

^f If positive urine test, serum pregnancy test will be done to confirm result.

^g Samples for hemoximetry will be obtained predose (within 30 minutes prior to dosing) at the investigational site.

^h Visits should take place in the morning. Participants are instructed to hold study drug until a predose blood sample for PK is obtained at the investigational site.

ⁱ During the observation period, the participant will receive their maximum tolerated dose or 3000 mg daily.

^j During the observation period, blood samples for PK will be obtained predose (within 30 minutes prior to dosing) at the investigational site.

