1.4. Summary of the Known and Potential Risks and Benefits of Voxelotor

Clinical data to date have shown that treatment with voxelotor results in a dose-dependent increase in Hb within 2 weeks that is maintained through 24 weeks, and with an associated decrease in clinical measures of hemolysis which correlates with drug exposure (Brown, 2018; Vichinsky, 2018). In a global, multicenter, Phase 3, double-blind, randomized, placebo-controlled trial of voxelotor in participants with SCD (Study GBT440-031), the percentage of participants achieving an Hb response (> 1 g/dL Hb increase from Baseline at Week 24) was dose dependent: 51.1% for the voxelotor 1500 mg group, 32.6% for the voxelotor 900 mg group, and 6.5% for the placebo group ($p < 0.001$ for each voxelotor dose vs placebo). In the 1500 mg group, the mean Hb increase at Week 24 was 1.14 g/dL and in placebo -0.08 g/dL. Consistent with the improvement in Hb, the reductions in hemolysis measures (indirect bilirubin, absolute reticulocytes, percent reticulocytes, and LDH) were observed with both voxelotor 1500 mg and 900 mg compared to placebo. These were significant for indirect bilirubin (-25.9%, $p < 0.001$) and percent reticulocytes (-24.5%, $p < 0.001$) (Vichinsky, 2019).

Based on available data, voxelotor has been well tolerated in adult and adolescent patients with SCD. The most common adverse reactions in participants with SCD ≥ 12 years old in $\geq 10\%$ of participants treated with voxelotor 1500 mg with a difference of $> 3\%$ compared to placebo included headache, diarrhea, abdominal pain, nausea, fatigue, rash, and pyrexia. Other clinically relevant and less frequent adverse reactions included drug hypersensitivity ($< 1\%$). There were no reported events of anaphylaxis or anaphylactoid reactions in the clinical development program. The majority of treatment-emergent adverse events (TEAEs) were Grade 1 to Grade 2 in severity, clinically manageable, and reversed or resolved. Overall, the safety profile was similar in participants who were or were not receiving HU concomitantly, and between adults and adolescents. In SCD studies with voxelotor, the incidence of VOCs was similar to placebo

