8.5. Vital Signs

Vital signs (blood pressure, heart rate, and temperature will be measured, as outlined in Schedule of Assessments ([Appendix A](#), [Appendix B](#)), after a participant has rested comfortably for at least 5 minutes in the supine or sitting position, as age appropriate and feasible. A repeated measurement of any of the vital signs parameters will be taken within 5 minutes if the first reading is outside of the normal range and deemed clinically significant.

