10.4. Data Analysis

Data will be presented by maximum dose level.

A TEAE, defined as an event that occurs on or after Day 1 of study drug or the worsening of a pre-existing condition on or after Day 1 of study drug, will be classified according to the Medical Dictionary for Regulatory Activities (MedDRA). The incidence of TEAEs and relatedness to study drug, as assessed by the Investigator, will be summarized descriptively by maximum dose level tolerated.

Clinical laboratory tests, ECGs, and vital signs over time will be summarized by maximum dose level tolerated using descriptive statistics. Change from baseline in ECG intervals will be evaluated using descriptive statistics. If an effect on mean change from baseline in QTc interval exceeding 10 msec is observed, concentration-QTc analysis may be explored. Results from the diagnostic interpretation will be summarized by maximum dose tolerated.

An Hb responder endpoint, defined as an increase in Hb of > 1 g/dL compared to Baseline, will be summarized. Additionally, change from baseline in hemoglobin and clinical measures of hemolysis (unconjugated bilirubin, % reticulocyte, absolute reticulocyte, and LDH) will be summarized by maximum dose level tolerated using descriptive statistics.

The incidence of VOCs will be summarized by maximum dose tolerated.

The CGI-C and PGI-C will be summarized by maximum dose level tolerated.

Population PK analysis using nonlinear mixed-effect modeling will be performed to characterize voxelotor PK in plasma, and whole blood.

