^b Vital signs (heart rate, blood pressure, and body temperature [only on Day 1] will be measured after a participant has rested for at least 5 minutes in the seated or supine position. While at the investigational site, vital signs will be obtained in the morning prior to dosing and other planned assessments.

^c Triplicate ECGs should be recorded at screening. On Day 1 of Period 1 only, triplicate ECGs should be recorded at 3 timepoints prior to dosing (-45 min, -30 min, and -15 min); the predose PK sample should be collected immediately prior to the -30-minute ECGs; and postdose triplicate ECGs (after the morning dose) should be recorded within 15 min following the 2-hour PK sample collection. On Day 1 in Periods 2, 3, and 4, on Day 7 in all periods, and on Day 21 in Period 4, predose triplicate ECGs should be recorded within 15 minutes following the predose PK sample collection. Postdose triplicate ECGs (after the morning dose) should be recorded within 15 min following the 2-hour PK sample collection. All triplicate ECGs will be centrally read. Participants should rest supinely for at least 10 min prior to ECGs.

^d A complete physical examination should be performed at the Screening visit; Physical examinations after the Screening visit may be abbreviated. Abbreviated physical examination should include at a minimum: Examination of skin, cardiovascular and respiratory systems, abdominal examination, and symptom-directed examination.

^e If positive urine test, serum pregnancy test will be done to confirm result.

^f A test for HIV will be performed only if clinically indicated.

^g On Day 1, samples for hemoxygometry will be obtained predose (within 30 minutes prior to dosing) and at 8 hours postdose. Samples will only be predose on all other scheduled days. The predose sample will be obtained prior to dosing at the investigational site.

^h Visits should take place in the morning. Participants are instructed to hold study drug until a predose blood sample for PK is obtained at the investigational site.

ⁱ During Period 1 (1500 mg daily), study drug will be administered as 3 × 500 mg tablets once daily. During Periods 2, 3, and 4, study drug will be administered BID (Period 2: 2000 mg daily, 2 × 500 mg BID; Period 3: 2500 mg daily, 3 × 500 mg in morning and 2 × 500 mg in evening); Period 4: 3000 mg daily, 3 × 500 mg BID).

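### As scheduled, body temperature is never recorded on 3000 mg/day: the vital-sign footnotes in Appendices A and B do not match Section 8.5

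*Combined protocol and SAP*

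**What the plan says.** Three places in the protocol define the vital-sign set, and they differ.

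- Section 8.5 includes temperature without limiting the day: "Vital signs (blood pressure, heart rate, and temperature will be measured, as outlined in Schedule of Assessments". It refers to both appendices for timing.
- Appendix A footnote b, for dose escalation, restricts it: "Vital signs (heart rate, blood pressure, and body temperature [only on Day 1] will be measured after a participant has rested". The same footnote fixes the time of day: "vital signs will be obtained in the morning prior to dosing and other planned assessments".
- Appendix B footnote c, for the observation period and safety follow-up, leaves temperature out: "Vital signs (heart rate and blood pressure) will be obtained in the morning prior to dosing and other planned assessments".

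Appendix B footnote b says of the first observation day: "Day 1 of the observation period is the same as the last day of the dose escalation period". After a dose reduction a separate Day 1 visit is held, "which would collect the same assessments as the Day 21 visit in the Dose Escalation Period (Appendix A").

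Section 1.4 reports that the common adverse reactions at 1500 mg (in at least 10% of participants and more than 3% above placebo) "included headache, diarrhea, abdominal pain, nausea, fatigue, rash, and pyrexia". Section 9 requires vital-sign changes from baseline that are judged clinically significant to be recorded as adverse events. Section 10.4 plans the summary: "Clinical laboratory tests, ECGs, and vital signs over time will be summarized by maximum dose level tolerated using descriptive statistics".

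**The concern.** The primary objective (Section 2.1) is tolerability and safety at 2000 to 3000 mg/day. The study rationale (Section 1.5.1) adds that results will be compared with those at 1500 mg. Temperature is the vital sign most directly tied to a reaction the protocol already names, yet it is the one dropped as the dose rises. Because the Day 1 reading comes before the morning dose, it belongs to the dose just finished and not to the one about to start. The highest dose has no later period whose Day 1 could supply its reading.

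Two uses of the data are affected. The Section 10.4 summary would contain no temperature measured on 3000 mg/day. The Section 9 rule, and the repeat-measurement rule in Section 8.5, could not be triggered at that dose by a scheduled temperature.

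**Working it through.** The plan gives no figure to reproduce, and no power or error-rate calculation applies. The check is a count of scheduled readings, each assigned to the dose taken up to that moment.

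**Inputs**
- Vital-sign marks in Appendix A: Screening and Days 1, 2 and 14 of each period; none on Days 3, 7 or 21. This is read by column position from the extracted table.
- Vital-sign marks in Appendix B: Days 7, 21, 42, 84, 126, 168 and 196; Day 1 is blank.
- Temperature: Day 1 only in Appendix A, before the morning dose; not listed in Appendix B.
- Periods (Section 3.2): 1500, 2000, 2500 and 3000 mg/day for 3 weeks each, then 24 weeks at the tolerated dose or 3000 mg/day.

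**Step 1. Dose behind each scheduled temperature**

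| Reading | Dose taken up to then |
|---|---|
| Period 1 Day 1 | none |
| Period 2 Day 1 | 1500 mg/day |
| Period 3 Day 1 | 2000 mg/day |
| Period 4 Day 1 | 2500 mg/day |

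That makes 4 readings, 3 of them on drug and 0 on 3000 mg/day. Each on-drug reading exists only for participants who go on to the next period. Someone who cannot tolerate 2500 mg/day and steps down gives no scheduled temperature on 2500 mg/day.

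**Step 2. Could observation Day 1 supply a reading?** No. It has no vital-sign mark. It coincides with the last escalation day or, after a dose reduction, repeats the Appendix A Day 21 visit, which has no vital-sign mark either.

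**Step 3. Vital-sign visits on 3000 mg/day**
- Period 4: Days 2 and 14 = 2.
- Observation: Days 7, 21, 42, 84, 126 and 168 = 6.
- Total 2 + 6 = 8, of which 0 include temperature. Planned time at the dose is 3 + 24 = 27 weeks (27 × 7 = 189 days).

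**Step 4. Sensitivity to wording.** If Day 1 in footnote b meant Period 1 only, there would be 1 reading, off drug, and still 0 on 3000 mg/day. The zero follows from the footnotes alone; only the denominator of 8 depends on the column reading.

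**Step 5. Observation at the other doses.** Footnote c applies to everyone, so no participant has a scheduled temperature in the 24 observation weeks, whatever the dose.

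**Step 6. After the change proposed below.** On-treatment readings for a participant who completes at 3000 mg/day would be 3 each at 1500, 2000 and 2500 mg/day (Days 2 and 14, and Day 1 of the next period) and 8 at 3000 mg/day: 3 × 3 + 8 = 17. Adding Screening, Period 1 Day 1 and Day 196 gives 20, against 4 now, so 20 − 4 = 16 more.

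**The case against.** The strongest reply is that fever has another route into the data. The primary endpoints are treatment-emergent and serious adverse events, not temperature. Section 9 requires participants to be asked about new or ongoing events at each visit, each escalation period has a Day 3 wellbeing call (Section 8.14), and Section 8.4 allows symptom-directed examination. That stands. A reader might infer that fever on 3000 mg/day would go undetected unless the participant volunteered it, or that the primary endpoint is compromised. The documents support neither: questioning about events is active and is planned at every dose.

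Second, the imbalance is small in absolute terms: at most one predose spot reading at each lower dose against none at 3000 mg/day. Even 8 readings in 189 days cover 8/189 = 4.2% of days, so they would not characterise an intermittent sign. This also stands, and it limits the severity. It does not explain why heart rate and blood pressure are taken at those visits and temperature is not.

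Third, the Day 1 restriction is explicit and may be deliberate, and no study stopping rule or dose-limiting criterion uses a temperature threshold. In Appendix C fever appears only as a clinical sign accompanying raised ALT. But no reason for the restriction is given, and Section 8.5 lists temperature without it, so the passages need reconciling whatever was intended.

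A reader might also infer that the Section 10.4 table would give false reassurance about 3000 mg/day. That goes too far. There are no table shells, and a display by visit would show the gap. Grouping by maximum tolerated dose affects every safety parameter, not temperature alone. Nor are readings missing in the usual sense, because none were scheduled.

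**Conclusion.** The point holds as a gap in scheduled measurement and an inconsistency among Section 8.5, Appendix A footnote b and Appendix B footnote c. As written, 0 of 8 on-treatment vital-sign visits at 3000 mg/day include temperature, against at most one reading on each of 1500, 2000 and 2500 mg/day. The zero rests on the literal wording of the two footnotes and does not depend on how Day 1 is read; the count of 8 assumes the column alignment given above.

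The loss is confined to objective temperature data at the highest dose, for the vital-signs summary and for adverse-event recording triggered by a measured change. Adverse-event capture of pyrexia is intact. It would also be wrong to say that the primary objective itself requires a comparison with 1500 mg; that comparison is stated in the study rationale. Severity is minor to moderate: the consequence is limited, but it falls at the top of the dose range under study and is nearly free to correct.

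**What to change.** Reconcile the three places so that the vital-sign set is the same at every dose level:

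- In Appendix A footnote b, delete the bracketed Day 1 restriction.
- In Appendix B footnote c, add body temperature to heart rate and blood pressure.
- Leave Section 8.5 as it is; it would then agree with both schedules.
- In Section 10.4, state that temperature is summarized by the dose being taken at the reading, so that a predose Day 1 value is attributed to the preceding dose.

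The cost is one extra data field at visits where vital signs are already taken: up to 16 further readings for a participant who completes at 3000 mg/day, and at most 16 × 40 = 640 across the maximum enrolment. No visit is added. If the sponsor prefers to keep the restriction, the protocol should give the reason, align Section 8.5 with it, and state that temperature on 3000 mg/day is not measured on schedule and that fever there is assessed through adverse-event reporting.

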APPENDIX C. DOSE MODIFICATION GUIDELINES FOR STUDY DRUG-RELATED ADVERSE EVENTS

Dose Reduction	
Event	Recommended Action
Grade \geq 2 (NCI grading scale) AE deemed considered related to study drug by the Investigator AND Precludes continued dosing at the current dose level due to safety concern or lack of tolerability (in the Investigator's judgment)	Study drug: May be reduced by one (1) tablet. If, in the opinion of the Investigator, a Grade 2 AE has resolved to \leq Grade 1, participant may resume study drug at the original dose. If, in the opinion of the Investigator, the AE poses a significant safety concern such that a dose hold is considered, the Investigator should contact the Medical Monitor.
ALT $\geq 3 \times$ ULN if ALT within normal limits at baseline OR $> 3 \times$ ULN AND a ≥ 2-fold increase above baseline value if elevated ALT value at baseline in the absence of additional signs of compromised liver function such as elevated PT, PTT, INR, elevated conjugated bilirubin, jaundice, or hepatic pain	Study drug: Confirm by repeat testing within 48 to 72 hours if possible, then repeat liver panel at least weekly until ALT level improves. Additional Actions: If ALT level continues to increase, reduce dose by one tablet and notify the Medical Monitor.
ALT $\geq 5 \times$ and $< 8 \times$ ULN (confirmed by repeat testing within 48 to 72 hours) in the absence of additional signs of compromised liver function such as elevated PT, PTT, elevated conjugated bilirubin, jaundice, or hepatic pain	Study drug: Reduce dose by one tablet. Additional actions: Repeat liver panel test within 48 to 72 hours if possible and then at least weekly until resolution to $< 5 \times$ ULN; if ALT does not improve within 2 weeks of dose reduction, the Medical Monitor should be notified. If ALT continues to increase within 1 week after a dose reduction, dose should be interrupted and the Medical Monitor should be notified.
Dose Interruption (Hold)	
Event	Recommended Action
Grade ≥ 3 (NCI grading scale) AE deemed considered related to study drug by the Investigator AND Precludes continued dosing at the current or at a reduced dose level due to safety concern or lack of tolerability in the Investigator's judgment	Study drug: Hold dose until \leq Grade 2, then resume study drug at original dose. If, in the opinion of the Investigator, dosing should be resumed at a lower dose, contact the Medical Monitor for further discussion. If the AE recurs or worsens, reduce dose by one tablet. Maximum dose hold is 5 continuous days. If, in the opinion of the Investigator, a longer dose hold is clinically needed, the Medical Monitor should be contacted for discussion.

Dose Interruption (Hold) (continued)	
Event	Recommended Action
NOTE: Study drug-related rash Grade 2 study drug-related rash that persists after a dose reduction	
Management: Consider antihistamines, topical steroids, as clinically indicated.
 
Study Drug: If rash does not resolve or improve to Grade 1 after a dose reduction, consider a dose hold. Once the rash has resolved or improved, dosing may be resumed at the reduced level or if, in the opinion of the Investigator, participant may resume study drug at the original dose. The Medical Monitor may be contacted for further discussion.
 
Maximum dose hold is 5 continuous days. If, in the opinion of the Investigator, a longer dose hold is clinically needed, the Medical Monitor should be contacted for discussion.

Drug Discontinuation	
Event	Recommended Action
Grade ≥ 3 study drug-related AE that, at the discretion of the Investigator, warrants discontinuation of study drug (eg, has not improved or resolved after dose hold).	
Study drug: Discontinue study drug. If the Investigator considers that the participant would benefit from continuing treatment, the Medical Monitor should be contacted.

Consider drug discontinuation if: 
 • ALT $> 8 \times$ ULN • ALT $> 3 \times$ ULN or ≥ 2-fold increase above baseline value if elevated ALT value at baseline with additional signs of compromised liver function such as elevated PT, PTT, INR, elevated conjugated bilirubin, jaundice, or hepatic pain, appearance of fatigue, nausea, vomiting, right upper quadrant pain or tenderness, fever, rash, and/or eosinophilia. 	
Study drug: Hold dose, confirm by repeat testing within 48 to 72 hours if possible, and assess potential reversible causes of liver function test abnormalities. Contact the Medical Monitor for discussion of study drug discontinuation.

AE, adverse event; ALT, alanine aminotransferase; INR, international normalized ratio; NCI, National Cancer Institute; PT, prothrombin time; PTT, partial thromboplastin time; ULN, upper limit of normal.

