3.7.3. Early Discontinuation of Individual Participants

3.7.3.1. Individual Dose-limiting Toxicity Definition: Dose Escalation Period

Criteria for individual dose-limiting toxicity at doses beyond 1500 mg/day include, but are not limited to, the following:

- Any AE Grade ≥ 3 not clearly resulting from the underlying disease and deemed by the Investigator and/or Medical Monitor to be related to study drug.
- Worsening of an ongoing, treatment-related AE by ≥ 1 grade as per Investigator assessment
- Grade 3 nausea, vomiting, or diarrhea (deemed related to study drug) requiring hospitalization and/or intravenous fluids and parenteral tube feeding, total parenteral nutrition
- Study drug-related SAE

If any of these criteria is met, the Investigator should consider temporary dose reduction and/or study drug discontinuation for the individual participant after discussing with the Sponsor. If a subject discontinues early due to AEs, the subject will not be eligible for the open-label extension study.

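### After a hold for a related Grade 3 or worse AE, Appendix C restarts the original dose at Grade 2 or less, a looser restart step than it sets after a Grade 2 AE

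*Combined protocol and SAP*

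**What the plan says.** Appendix C gives recommended actions for study drug-related AEs, arranged as reduction, interruption and discontinuation.

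- **Hold row.** The trigger is a related AE of Grade 3 or worse that, in the Investigator's judgment, "Precludes continued dosing at the current or at a reduced dose level due to safety concern or lack of tolerability". Dosing is held until the AE is Grade 2 or less. The instruction then reads "then resume study drug at original dose. If, in the opinion of the Investigator, dosing should be resumed at a lower dose", followed by a request to contact the Medical Monitor. The same cell adds: "If the AE recurs or worsens, reduce dose by one tablet. Maximum dose hold is 5 continuous days", with a longer hold to be discussed with the Medical Monitor.
- **Reduction row.** The trigger is a related AE of Grade 2 or worse that "Precludes continued dosing at the current dose level due to safety concern or lack of tolerability". The dose may be cut by one tablet. For a Grade 2 AE that has resolved to no worse than "Grade 1, participant may resume study drug at the original dose". The row's last sentence asks the Investigator to contact the Medical Monitor if the AE is a significant enough safety concern that a hold is being considered.
- **Rash row.** This applies to a Grade 2 related rash that persists after a reduction and leads to a hold. "Once the rash has resolved or improved, dosing may be resumed at the reduced level or if, in the opinion of the Investigator" agrees, at the original dose.
- **Discontinuation row.** A related Grade 3 or worse AE may end treatment, for example one that "has not improved or resolved after dose hold".

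Section 3.7.3.1 treats a related Grade 3 or worse AE above 1500 mg/day in escalation as a dose-limiting toxicity, for which "the Investigator should consider temporary dose reduction and/or study drug discontinuation for the individual participant after discussing with the Sponsor". Section 3.2, which cites Appendix C, asks for Medical Monitor consultation on dose modifications in the observation period.

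**The concern.** The two rows rank the events correctly at the first step and inconsistently at restart. In the hold row the Investigator has judged that neither the current nor a reduced dose is acceptable. The default restart nevertheless passes over the reduced dose and goes back to the full one, with the AE possibly still at Grade 2. Within that restart instruction, Medical Monitor contact is attached to the choice of a lower dose and not to the choice of the original one.

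At stake is a participant's re-exposure to a dose that has already produced a related Grade 3 or worse AE, before that AE has settled to the level the plan names after a milder event. This matters most above 1500 mg/day. Section 1.5.2 gives 1500 mg daily as the multiple-dose level reached so far, with 2800 mg given only as a single dose in healthy volunteers, and tolerability above 1500 mg/day is the primary objective.

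**Working it through.** The plan states no figure to reproduce. The check is a comparison of text, with a little arithmetic on scope.

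**Step 1. The two Appendix C rows side by side**

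| | Hold row | Reduction row |
|---|---|---|
| AE grade that triggers it | 3 or worse, related | 2 or worse, related |
| What the AE rules out | Current dose and a reduced dose | Current dose |
| First action | Stop dosing | Optional cut of one tablet |
| Grade for return to original dose | 2 or less | 1 or less (stated for a Grade 2 AE) |
| Force of the return wording | Directive | Permissive |

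The first action is stricter in the hold row. The restart grade is looser by 2 − 1 = 1 CTCAE grade, and the wording is firmer.

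**Step 2. Is a stricter restart grade set elsewhere?** Section 3.7.3.1 asks the Investigator to consider reduction or discontinuation but gives no grade for resuming. Section 3.2 allows a lower level after intolerance and consultation on modifications, again with no restart grade. The discontinuation row covers AEs that fail to improve. The rash row requires only that the rash has resolved or improved. It offers the reduced level first, and the original dose if the Investigator so judges. That parallel is partial, because a reduction has already been tried. No section sets a stricter restart grade.

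**Step 3. Does a one-tablet-lower restart land on a planned dose?** With 500 mg tablets:

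- 3000 − 500 = 2500 mg/day; 500/3000 = 16.7% lower
- 2500 − 500 = 2000 mg/day; 500/2500 = 20.0% lower
- 2000 − 500 = 1500 mg/day; 500/2000 = 25.0% lower

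Each is a dose level in Section 3.2, and none falls below 1500 mg/day.

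**Step 4. Scope.** Using the nominal durations in Section 3.6 for a participant who reaches 3000 mg:

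- all dosing: 4 × 21 + 168 = 252 days
- above 1500 mg/day: 3 × 21 + 168 = 231 days; 231/252 = 91.7%
- hold limit: 5/21 = 23.8% of an escalation period, and 5/168 = 3.0% of the observation period

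These figures show where the rule would apply and how short a hold is. They do not measure how often it would be used or how much harm it would do. The only relevant statement is in Section 1.5.1: earlier treatment-related AEs were mostly Grade 1 or 2, at doses up to 1500 mg daily in the pivotal study.

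**The case against.** The strongest reply is that the rows are not like for like. Grade 2 alone triggers nothing in the reduction row; the AE must also rule out the current dose. A tolerable Grade 2 AE continues at full dose anyway, so restarting at Grade 2 is consistent, and a residual Grade 2 AE that still rules out the dose meets the reduction trigger. Part of this stands: the trigger is available. But the hold row does not point to it. The residual grade is also assessed while dosing is interrupted, after the original dose was not tolerated, so it does not show that the AE is tolerable on that dose.

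Three stronger readings are tempting, and the documents do not support them.

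- *A reader might infer that Appendix C is more lenient overall for the worse event.* It is not. A full hold is stricter than an optional one-tablet cut, and only the restart step is looser.
- *A reader might infer that full-dose restart happens without Medical Monitor or Sponsor involvement.* The reduction row's trigger includes Grade 3 or worse, and it asks for contact when a hold is considered for a significant safety concern. Section 3.7.3.1 asks for discussion with the Sponsor in escalation, and Section 3.2 for consultation on modifications in observation. None of this is expressly tied to the restart decision, but contact is likely within the same short episode.
- *A reader might infer a conflict with Section 3.7.3.1, or a distortion of the summaries by maximum dose tolerated.* A temporary reduction under that section allows a return to the original dose, and nothing in the documents shows an effect on the dose grouping.

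It is also true that the actions are recommendations, that recurrence or worsening brings a one-tablet cut, and that nothing in the documents shows the chosen threshold to be unsafe.

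**Conclusion.** The point holds for the restart step only. After a related Grade 3 or worse AE that ruled out even a reduced dose, the written default is the original dose at Grade 2 or less; after a Grade 2 AE, the condition for that dose is Grade 1 or less. The safeguards soften this without changing the default grade or dose.

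The conclusion assumes that sites will follow the hold row as worded and that the difference between the rows is not deliberate; the documents give no reason for it. The size is one CTCAE grade at restart and one tablet of dose. How many participants would be affected cannot be derived, and the number is likely small. No effect on endpoints, sample size or analysis is claimed. This is a cheap improvement in participant safety.

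**What to change.** For doses above 1500 mg/day, reword the hold row as follows:

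1. Resume the original dose only once the AE is Grade 1 or less.
2. If the AE is still Grade 2 at restart, resume at one tablet less after Medical Monitor contact, and return to the original dose at Grade 1 or less.
3. State that this lower restart is a temporary reduction in the sense of Section 3.7.3.1. It does not by itself start the observation period or set the participant's maximum tolerated dose, unless the Investigator and Medical Monitor judge the original dose not tolerated.

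Item 3 is needed because Section 3.2 allows a dose not tolerated in escalation to be reduced to a previous level, which is then given for 24 weeks as the observation period. Appendix B adds a Day 1 visit when that period follows a reduction. Without item 3, a cautious restart could be read as that reduction and end escalation early.

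Leave the 1500 mg/day rule, the 5-day hold limit and the recurrence rule as they are. Because a residual Grade 2 AE can restart one tablet lower, the hold need not be lengthened.

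The cost is the wording of one cell with a cross-reference, and a few more Medical Monitor contacts, some of which the protocol already asks for. Some restarts will be later or one tablet lower, including for some residual Grade 2 AEs that would have been tolerated at the original dose. With item 3 in place, the change by itself adds no visits and alters neither the sample size nor the analyses.
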